13.1. INFORMED CONSENT

Written informed consent will be obtained from all subjects' parent or legal guardian, and whenever possible, verbal assent will be obtained as per IRB or EC guidelines before any study-related procedures (including any pre-treatment procedures) are performed. The investigator(s) has both ethical and legal responsibility to ensure that each subject's parent or legal guardian, and the child where possible, are being considered for inclusion in this study is given a full explanation of the protocol. This shall be documented on a written informed consent form, which shall be approved by the same IRB or EC responsible for approval of this protocol. Each informed consent form shall include the elements required by ICH, Part E6, Section 4.8 and any applicable local regulations. The investigator agrees to obtain approval from the Sponsor of any written informed consent form used in the study, preferably prior to submission to the IRB or EC.

Once the appropriate essential information has been provided to the subject and fully explained by the investigators (or a qualified designee) and it is felt that the subject understands the implications of participating, the subject's guardian or legally authorized representative and the investigator (or designee) shall sign and date the IRB- or EC-approved written informed consent form. The subject's parent or legal guardian, and the subject whenever possible, shall be given a copy of the signed and dated informed consent form, and the original shall be filed appropriately, according to the institution. A second copy may be filed in the subject's medical record, if allowed by the institution.

13.2. INSTITUTIONAL REVIEW BOARD/ETHICS COMMITTEE

This protocol, the written informed consent form and any materials presented to patients shall be submitted to the IRB or EC identified with this responsibility. Notification in writing of approval must come from the IRB or EC chairman or secretary, to the investigator, either as a letter or as a copy of the appropriate Section of the IRB or EC meeting minutes where this protocol and associated informed consent form were discussed. The investigator will not participate in the decision. If the investigator is an IRB or EC member, the written approval must indicate such non-participation in the voting session. The investigator will submit status reports to the IRB or EC as required by the governing body. The IRB or EC must be notified by the investigator in writing of the interruption and/or completion of the study; the investigator must promptly report to the IRB or EC all changes in research (protocol amendments) and will not make such

changes without IRB or EC approval, except where necessary to eliminate apparent immediate hazards to human patients. In cases where it is necessary to eliminate immediate hazards to patients, the IRB or EC must then be notified of the change as per local requirements. The investigator is required to maintain an accurate and complete record of all written correspondence to and received from the IRB or EC and must agree to share all such documents and reports with the Sponsor.

### **ABBREVIATIONS**

AE adverse event

ALT/SGPT alanine transaminase/serum glutamic-pyruvic transaminase

AST/SGOT aspartate transaminase/ serum glutamic oxaloacetic transaminase

AUC area under the curve

 $AUC_{inf}$  area under the curve of the blood concentration to infinity  $AUC_{last}$  area under the curve of the blood concentration to the last

measurable concentration

BP blood pressure

BUN blood urea nitrogen
CI confidence interval

CL total clearance

CSR clinical study report

Cmax maximum peak plasma concentration

DBP dystolic blood pressure

dL deciliter

DSMB Data Safety Monitoring Board

eCRF electronic case report form
GPV Global Pharmacovigilence

h hour

HDL high density lipoprotein

HR heart rate

ITT intent-to-treat

IV intravenous

IVRS Interactive Voice Response System
IWRS Interactive Web Response System

kg kilogram

LDH lactate dehydrogenase LDL low-density lipoprotein

LLN lower limit of the standard reference (normal) range

MAP mean arterial pressure

max maximum

MDCO The Medicines Company

MedDRA Medical Dictionary for Regulatory Activities

mg milligram
min minimum
min minute

mmHg millimeter(s) of mercury
MRT mean residence time

M1 carboxylic acid metabolite

NONMEM Nonlinear Mixed-Effect Modeling PCS potentially clinically significant

PD pharmacodynamics PK pharmacokinetics

Q quartile

SAE serious adverse event
SAP statistical analysis plan
SAS statistical analysis system
SBP systolic blood pressure
SD standard deviation

sec seconds

SEM standard error of mean

 $t_{1/2}$  half-life

TBPR target blood pressure rate

TEAE treatment emergent adverse event

 $t_{max}$  time to reach maximum peak plasma concentration ULN upper limit of the standard reference (normal) range

U/L units per liter

VLDL very low density lipoprotein

Vss volume of distribution at a steady state

Vz volume of distribution based in the terminal phase

WHO World Health Organization

μg microgram

 $\lambda_z$  terminal rate constant

### 1. INTRODUCTION

### 1.1. TRIAL INTRODUCTION

This is a Phase IV open-label study in pediatric patients undergoing elective surgery requiring anesthesia  $\geq 1$  hour and for whom parenteral intravenous (IV) antihypertensive therapy for blood pressure (BP) management is expected for at least 30 minutes.

Approximately 80-100 patients are to be enrolled in a stepwise approach to ensure 80 patients can be evaluated for efficacy. Patients will be enrolled in a stepwise approach, starting with the adolescent cohort. An interim analysis of safety and dosing of the adolescent cohort will be performed before the initiation of the next cohort.

- Cohort 1: 20 adolescent patients (12 years to less than 18 years old)
- Cohort 2: 20 children (2 to less than 12 years, including 10 patients in each age group 6 to less than 12 years and 2 to less than 6 years)
- Cohort 3: 20 infants and toddlers (28 days to less than 24 months)
- Cohort 4: 20 preterm and newborn infants (0 to less than 28 days)

A Data Safety Monitoring Board (DSMB) will be set up to monitor the safety and dosing on an ongoing basis for all cohorts. Following the completion of each cohort starting with Cohort 1, the DSMB will review the safety and dosing data and make any safety recommendations to the Sponsor prior to enrolling the next cohort. The DSMB will determine if it is appropriate to proceed with enrollment of the next cohort, and whether adjustments in dosing scheme are required.

The investigator will pre-specify a target range for the desired reduction in systolic blood pressure (SBP) for each patient prior to drug exposure. This patient-specific target SBP range will be recorded via the interactive voice/web response system (IVRS/IWRS) and cannot be changed for the first 30-minute treatment period. The difference between the upper and lower limits of the specified target SBP range should be not less than 20 mmHg and not more than 40 mmHg.

Cohort 1 (ages 12 to less than 18 years) will receive an initial weight based dose of ; this rate will be maintained for the first 1.5 minutes. If the target SBP range is not achieved within 1.5 minutes, the clevidipine infusion rate may be up-titrated incrementally per the protocol dosing, progressing to up to the maximum dose of every 1.5 minutes until a SBP within the pre-specified target range is reached. The initial dose and the subsequent up-titration doses for Cohorts 2, 3 and 4 will be determined after an interim analysis of data from the preceding cohort. As the blood pressure approaches the desired range, dosing may be increased by less than doubling, and the time between dose adjustments may be

lengthened to greater than 1.5 minutes. If the target SBP range is achieved at any of the titration doses, that rate may be maintained for up to 96 hours to maintain the BP, or titrated up or down as necessary to maintain SBP within the target range. Clevidipine infusion may be terminated at any time for safety reasons.

During the initial 30 minutes of the treatment period, clevidipine should be administered continuously as monotherapy. The use of an alternative IV antihypertensive agent is discouraged and should be limited to situations where it is medically necessary to maintain patient safety. If the desired BP control effect is not attained using the maximum dose of clevidipine, rescue therapy with the use of an alternative IV antihypertensive agent should be implemented.

After the first 30-minute treatment period, it may be necessary to alter the desired SBP target range over the course of the remaining treatment period. Any changes in the target range will be captured in the electronic case report form (eCRF).

Patients who receive alternative intravenous rescue therapy in addition to clevidipine may continue in the study. If transition from clevidipine to an oral antihypertensive agent is required, the clevidipine infusion may be down-titrated or terminated as appropriate to maintain the desired blood pressure. If the BP rises to an undesirable level upon cessation of clevidipine infusion, additional therapy may be administered or clevidipine infusion may be restarted (and continue until successful transition to an oral therapy has been achieved). Patients who receive prolonged clevidipine infusions and are not transitioned to other antihypertensive therapies should be monitored for the possibility of rebound hypertension for at least 8 hours after the infusion is stopped [Cleviprex Prescribing Information, 2011].

If treatment with an IV anti-hypertensive agent is still required after 96 hours of clevidipine therapy, the patient will be transitioned to an alternative IV antihypertensive agent according to the institutional standard of care.

The schedule of events/assessments is shown in Table 1 and the pharmacokinetic (PK) sampling time is shown in Table 2.

Table 1: Schedule of Events/Assessments

		Treatment Period		Follow-up Period  Post Study Drug Termination (up to 7 days after final dose)				
Study assessment	Screening Period 0 to -7 Days (prior to study drug initiation)	Treatment Phase 1 Initial Dosing 0 -1.5 minutes	Treatment Phase 2 Titration & Maintenance Phase >1.5 to 30 minutes & >30 minutes up to 96 hours	Treatment Phase 3 Transition & Termination Phase	Follow-up 1 Hour (+ 30 minutes	Follow-up 12 Hour (+ 30 minutes)	Follow-up 24 Hour (+ 30 minutes)	Follow-up 7- Day  (+ 1 day)
Informed consent	X 							
Medical history & Physical exam	X 							
Height & Weight	X 							
Prior Medications	X 							
BP (SBP, DBP) /HR	X2,3	X3	X 4,5	X 4,5	X e	X 6		
Pregnancy test	X2							
Hematology (Protocol Section 6.3)	X2							
Serum chemistry every 24 hours (Protocol Section 6.3)	X 		Х		X 			
SBP Target Range	X 		X 					
Enrollment via IVRS/IWRS	X 							
Study drug administration		X 	X 	X 				
PK sampling	X3,8	X3,8	X8	X8	X8			
Concomitant Medications		Х	Χ	Х	Х	Х	Х	
Oral Antihypertensive Administration				Х				
AE and SAE reporting	<del></del>			X12 —				$\rightarrow$

 Written informed consent from parent or legal guardian and verbal assent (as per institutional policy) before initiation of any study-related procedures.

The Medicines Company Version 0.1, May 20, 2014

<sup>2 Assessment(s) must be performed prior to treatment to determine eligibility for enrollment into the study.

<sup>3 BP (SBP, DBP) and hear rate (HR) are measured using an intra-arterial catheter with electronic transducer. PK Sample 1 is to be taken up to 30 minutes prior to start of clevidipine infusion with BP and HR measured, immediately followed by PK Sample 1 collection. Baseline BP and HR are recorded at 60 sec, 45 sec, 30 sec, and 0 sec prior to initiation of clevidipine. PK Sample 2 is taken at 1.5 minutes after the start of clevidipine infusion (before first dose titration) with BP and HR measured, immediately followed by PK Sample 2 collection. The actual time of BP, HR and PK sample must be recorded using devices that are time synchronized.

-  BP and HR will be recorded every 1.5 minutes (+ 30 second window where a PK sample is required) for a period of at least 30 minutes, every 10 minutes for the next hour, every 30 minutes for the next 2 hours and every 1 hour until study drug is terminated (up to 96 hours). BP and HR will also be recorded immediately before each PK blood draw (Table 2) is obtained.
-  If a dose adjustment is indicated, BP and HR should be recorded just prior to each study drug dose change as well as every 1.5 minutes for 15 minutes after the dose adjustment, then return to the BP assessment schedule just prior to the dose adjustment.
-  BP and HR will be recorded every 1 hour until study drug has been stopped for 12 hours post-study drug termination.
-  Clevidipine administered as a continuous IV infusion.
- 8 Blood samples for PK analysis will be obtained from an arterial line per the time intervals included in Table 2 below (1 before clevidipine infusion; 4-5 during clevidipine infusion; 4 post clevidipine infusion). NOTE: BP and HR will be recorded immediately before each PK blood draw. The actual time of BP, HR and PK sample must be recorded using devices that are time synchronized.
- 9 Beyond the first 30-minute treatment period, it may be necessary to alter the desired SBP target range over the course of the remaining treatment period. Any changes in the target range will be captured in the case report form (eCRF).
-  The 7 day (+1 day) follow-up can occur by phone, if applicable.
- . Serum chemistry within 1 (+30 minutes) hour after study drug termination
- 12. AE and SAE reporting will be from time of consent through 7 days day) following termination of study drug infusion.

### Table 2: PK Sampling Times

Sample	Time point
1	Up to 30 minutes prior to start of clevidipine infusion
2	1.5 minutes post initiation of clevidipine infusion (before first dose titration)
3	1.5 minutes after first dose titration (must be performed before proceeding to second dose titration)
4	Once target SBP range is reached or 30 minutes after the initiation of clevidipine infusion, whichever comes first
5 (if applicable)	If transition to an additional antihypertensive is desired and concurrent administration is needed, a sample should be taken right before beginning administration of the additional antihypertensive agent
6	Right before the termination of the clevidipine infusion
7	0.5 minutes post termination of the clevidipine infusion
8	3 minutes post termination of the clevidipine infusion
9	15 minutes post termination of clevidipine infusion
10	1hour (+30 minutes) post final termination of the clevidipine infusion

The Medicines Company Version 0.1, May 20, 2014

### 2. OBJECTIVES

### 2.1. PRIMARY OBJECTIVE

The primary objective of this study is to evaluate the dosing, efficacy and safety of an intravenous (IV) infusion of clevidipine for blood pressure (BP) management in pediatric patients in the perioperative setting.

### 2.2. SECONDARY OBJECTIVES

The secondary objectives of the study are to evaluate additional efficacy, safety and dosing parameters associated with IV infusion of clevidipine for BP management in pediatric patients in the perioperative setting.

### 2.3. EXPLORATORY OBJECTIVES

Efficacy will be evaluated in the subgroups of patients with and without pre-existing hypertension. Additional analyses may be performed for efficacy and/or safety when applicable.

### 3. STUDY POPULATIONS

Three patient populations will be considered in the statistical analyses of this study.

### 3.1. SAFETY POPULATION

The safety population consists of all patients who are dosed with any study drug. This will be the primary population used for the safety analyses.

### 3.2. INTENT-TO-TREAT (ITT) POPULATION

The ITT population consists of all patients who are dosed with any study drug and have baseline and at least one post-baseline SBP measurement. This will be the primary population used for the efficacy analyses.

### 3.3. PHARMACOKINETICS/PHARMACODYNAMICS (PK/PD) POPULATION

The PK/PD population consists of all patients who are dosed with any study drug, have at least one documented and evaluable blood concentration and/or SBP observation and documented dose records. This will be the primary population for PK/PD analyses.

### 4. GENERAL STATISTICAL METHODOLOGY

All statistical analyses and summary information will be generated according to this statistical analysis plan (SAP). Any deviations from this SAP will be documented in the clinical study report (CSR).

Patient disposition, demographic and background characteristics will be presented for the safety, ITT and PK/PD populations. Unless otherwise specified, all efficacy analyses will be performed using the ITT population, all safety analyses will be performed using the safety population and all PK/PD analyses will be performed using the PK/PD population.

Continuous variables will be summarized using descriptive statistics including the number of patients reflected in the calculation (n), mean, standard deviation (SD), median, interquartile range (Q1 and Q3), minimum (min), and maximum (max). Frequencies and percentages will be displayed for categorical variables.

Because of the descriptive nature of this study, no formal statistical hypothesis testing will be performed. However, p-values and/or two-tailed 95% confidence intervals may be generated to demonstrate the strength of the findings whenever appropriate.

All data will be summarized for overall and by age cohort. Data listings will be provided for all data collected in the eCRF.

Unless otherwise specified for repeat pre-baseline assessments, the results from the final assessment made before or at the start of study medication will be used as baseline. If post-baseline assessments are repeated or unscheduled, the non-missing values from the first assessment will be used for generating summary statistics.

Unless otherwise specified (eg, in Section 8), missing data will not be imputed and will be excluded from the associated analysis.

### 5. PATIENT DISPOSITION AND STUDY COMPLETION

The number of patients included in each study population (i.e., safety, ITT and PK/PD) will be presented. The number and percentage of patients who completed and discontinued from the study, as recorded on the patient "End of Study" page of the eCRF, will be displayed for the three study populations. Reasons for discontinuation will be summarized descriptively.

The number of patients included in each of three study populations for each study center will be tabulated.

Listings of populations, discontinuation from the study along with the reason, will be provided by age cohort.

### 6. DEMOGRAPHICS AND BASELINE CHARACTERISTICS

Demographics including sex, age, ethnicity, height, weight, and BMI, baseline characteristics including blood pressure and heart rate, relevant medical history, as well as relevant past surgical/interventional procedure will be summarized with descriptive statistics for all populations (safety, ITT and PK/PD).

Listings of demographics, baseline characteristics, medical history and surgical/interventional procedures will be presented for each patient, including those who are enrolled but not treated with the study medication.

### 7. PROTOCOL DEVIATION

Any protocol deviations that occur during the study will be recorded in the eCRF. The number and percentage of patients who had at least one protocol deviation will be summarized by violation type.

### 8. EXTENT OF STUDY DRUG EXPOSURE

Study drug exposure will be summarized using the safety population by the following timeframes.

- 1. From initiation to the end of the first 30-minute treatment period, representing the protocol-specified initial and titration phases
- 2. From the end of the first 30-minute treatment period to the end of treatment, representing the protocol-specified maintenance phase
- 3. From initiation to the end of treatment, representing the overall treatment period

Exposure will be quantified and descriptively summarized using the following variables.

For timeframes 1 only:

- Receive at least 30 minutes of continuous clevidipine monotherapy (yes/no)
- Reason if did not receive at least 30 minutes of clevidipine monotherapy (SBP Target Range not reached, Adverse Event/Serious Adverse Event, Other)
- o Attempted maximum allowed dose CCI within 30 minutes of clevidipine infusion if did not receive at least 30 minutes clevidipine monotherapy (yes/no)

For timeframes 1 and 3 only:

- Number of patients who initiated the study drug infusion before surgery (yes/no)
- Primary reason for initiating study drug (Treatment for pre-existing hypertension, Controlled hypotension during surgery, Treatment for intra-operative hypertension, Control post-surgical hypertension)
- Initial infusion rate (μg/kg/min)

For timeframe 3 only

- o Reason for termination of IV clevidipine infusion
- IV clevidipine infusion successfully terminated at the first attempt (i.e., was not restarted) (yes/no)
- o Overall infusion duration (h)

For timeframes 1, 2 and 3

- Maximum infusion rate (μg/kg/min)
- Median infusion rate (μg/kg/min )

- On-drug infusion duration (h) (the summation of the durations of all the time segments when clevidipine was administered with an infusion rate of  $> 0 \,\mu\text{g/kg/min}$ )
- o Total dose infused (mg)
- Average infusion rate (μg/kg/min) (equals the total dose infused divided by on-drug infusion duration in minutes and baseline weight in kg)

Missing infusion rates will be imputed by linear interpolation between two observed infusion rates when the associated infusion start and stop times are observed. No missing rates will be imputed by extrapolation.

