1.4. DOSE RATIONALE

A population pharmacokinetic (PK) and pharmacodynamic (PD) model has been developed to describe the physiologic response (i.e., drop in systolic blood pressure, SBP [mmHg]) to clevidipine exposure in pediatric patients with moderate to severe acute hypertension.

Various dose regimens were simulated in pediatric patients with weights ranging from 2.5 kg up to 50 kg. CCI

Adolescent patients (ages 12 to less than 18 years) will receive weight based doses ranging from **CC** to a maximum of **CC** . The appropriateness of lower starting weight-based doses of **CC** and **CC** an

The above dosing rationale is supported by recently published case studies of the use of clevidipine in children [Tobias and Hoernschemeyer⁷].

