10.3.2. Efficacy Analysis

10.3.2.1. Primary Efficacy Endpoints

The primary efficacy endpoints of this trial are:

- Median time and dose to attain the initial prespecified target SBP range (minimum of 20 mmHg and a maximum of 40 mmHg apart) during the first 30 minutes of clevidipine infusion
- Percentage of patients achieving the initial prespecified target SBP range during the first 30 minutes of clevidipine infusion

Median time is the median of the time in minutes between the initiation of study medication and time the patient first achieves the initial prespecified target SBP range (TBPR) during the first 30 minutes of clevidipine infusion. The median time will be summarized using the Kaplan-Meier method. Median time will be estimated with a two-tailed 95% confidence interval. If patients do not reach TBPR within 30 minutes from the initial treatment with study medication, or another intravenous antihypertensive agent is administered, the patient will be considered censored at 30 minutes or the time when another intravenous antihypertensive agent is given, whichever comes first.

The percentage of patients achieving TBPR will be calculated using the number of ITT patients achieving the endpoint divided by the total number of ITT patients, and multiplied by 100.

Number and percent of patients achieving TBPR during the first 30 minutes along with the calculated 95% confidence interval will be presented.

Analysis of the infusion rate, total dose infused, and total volume infused at the time of first achieving TBPR during the first 30 minutes will be summarized descriptively.

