#### 10.1. PRIMARY EFFICACY ANALYSIS

• The time to and percent of patients who attain the initial pre-specified SBP target range within the first 30 minutes of study drug initiation.

The time to attain the initial pre-specified SBP target range is in minutes and is the duration between the initiation of study medication and the time a patient first achieves the initial pre-specified target SBP range (TBPR) during the first 30 minutes of clevidipine infusion. The time will be summarized using descriptive statistics and the Kaplan-Meier curve. The estimated median time with its two-tailed 95% confidence interval (CI) [Simon and Lee, 1982] will be presented. If a patient does not reach TBPR within 30 minutes from the initial treatment with study medication, or another antihypertensive agent is administered, the patient will be considered censored at 30 minutes or the time when another antihypertensive agent is given, whichever comes first.

The percentage of patients achieving the TBPR will be calculated using the number of ITT patients achieving TBPR divided by the number of ITT patients, and multiplied by 100. Two-tailed 95% CIs will be computed for these percentages.

• The dose to attain the initial pre-specified target SBP range (minimum of 20 mmHg and a maximum of 40 mmHg apart) during the first 30 minutes of clevidipine infusion.

The dose to attain the initial pre-specified target SBP consists of the infusion rate  $(\mu g/kg/min)$ , total dose (mg) infused, and number of titrations made when TBPR is reached.

The summary statistics on infusion rate, total dose infused, and number of titrations made when TBPR is reached will be presented.

All the aforementioned analyses will be performed using the ITT population and also for data exploration using the safety population.

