# 10.2.5. Percent change in SBP from baseline at each time point during the 30 minutes of clevidipine infusion, at each hour after the first 30 minutes of clevidipine infusion up to the cessation of infusion, and over the first 12 hours post study drug termination

Blood pressure will be measured every 1.5 minutes for the first 30 minutes of infusion, every 10 minutes in the next hour, every 30 minutes for the next 2 hours then every hour until the study drug is terminated or maximum 96 hours from initiation of study drug is reached, whichever is earlier. Blood pressure will also be measured just prior to each PK blood draw and each dose adjustment, as well as every 1.5 minutes for 15 minutes after the dose adjustment. After termination of the clevidipine infusion, blood pressure will be taken every 15 minutes for the first hour, then every hour for a maximum of 12 hours.

Descriptive statistics on changes and percent changes from baseline in SBP will be summarized at each specified timepoint. A graph will be presented on percent change in SBP during the first 30 minutes after initiation of study medication by age cohort.

Individual patient graphs will present SBP across all timepoints along with the study drug dose levels in mg/h.

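### SAP 8 omits the mg-to-μg factor from its average infusion rate (1,000-fold for the stated unit), and the overall summary of total dose in mg, one of three primary dose components, largely tracks body weight

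*SAP*

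**What the plan says.** **Exposure (SAP 8).** Total dose infused is listed in mg and on-drug duration in hours. The next item is the average infusion rate, labelled μg/kg/min, which "equals the total dose infused divided by on-drug infusion duration in minutes and baseline weight in kg". Maximum, median and initial infusion rates are also in μg/kg/min.

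**Primary dose endpoint (SAP 10.1).** "The dose to attain the initial pre-specified target SBP consists of the infusion rate", in μg/kg/min, together with "total dose (mg) infused, and number of titrations made when TBPR is reached". Protocol 10.3.2.1 plans an "Analysis of the infusion rate, total dose infused, and total volume infused at the time of first achieving TBPR during the first 30 minutes" and gives no units.

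**Level of summary (SAP 4).** All data are summarised overall and by age cohort. The cohorts run from preterm and newborn infants to patients just under 18 years.

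**Dosing basis.** SAP 1.1 and Protocol 3.1 describe a weight-based starting dose for adolescents. Protocol 3.1 carries the scheme to later cohorts unless earlier data call for a change. Protocol 1.4 reports simulations in "pediatric patients with weights ranging from 2.5 kg up to 50 kg".

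**Patient graphs (SAP 10.2.5).** "Individual patient graphs will present SBP across all timepoints along with the study drug dose levels in mg/h".

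**The concern.** Two separate points meet here.

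The first is dimensional. The average-rate definition states minutes explicitly although duration is listed in hours, so its authors were spelling out the conversion. They converted time and not mass. SAP 4 says that the analyses follow the SAP, so the definition itself should be right.

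The second is interpretive. When the drug is dosed per kg, a total in mg is the per-kg dose multiplied by weight. Pooled from newborns to adolescents, its mean or median depends heavily on the mix of body sizes. The trial is meant to inform paediatric dosing, and a reader of the overall row could take a figure that mostly reflects weight for a dose requirement.

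**Working it through.** The plan gives no numerical result for either quantity, so there is no figure to reproduce. Doses are redacted. The rate of 1 μg/kg/min used below is purely illustrative, and the ratios do not depend on it.

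**1. Unit check on SAP 8.** For a constant rate r (μg/kg/min), weight w (kg) and time T (min):

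- Total dose in mg = r × w × T / 1000.
- SAP rule as written = total mg / T / w = r / 1000.

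With r = 1, w = 10 and T = 30, total dose = 0.3 mg, and 0.3 / 30 / 10 = 0.001. The label requires 1. Multiplying by 1,000 returns the input rate. The same holds for r = 0.5, 1 and 3.5 at 2.5, 10, 25 and 50 kg: the shortfall is always 1,000-fold.

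**2. Total dose at equal per-kg dosing (r = 1, T = 30).**

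| Weight | Total dose | Rate | Total dose per kg |
|---|---|---|---|
| 2.5 kg | 0.075 mg | 0.15 mg/h | 0.03 mg/kg |
| 50 kg | 1.5 mg | 3.0 mg/h | 0.03 mg/kg |
| Ratio | 20 | 20 | 1 |

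**3. Share of the overall spread due to weight.** On the log scale, total mg = dose per kg + weight. If the two are independent, the share is Var(log w) / (Var(log w) + s²), where s is the log-SD of dose per kg.

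Assumptions (none of these is in the documents): median weights of 3, 8, 20 and 55 kg, within-cohort log-SD of weight 0.25, and s between 0.6 and 1.0. Cohorts are of equal size, as planned (20 each).

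- Logs of the medians: 1.099, 2.079, 2.996, 4.007; mean 2.545.
- Between-cohort variance: (2.093 + 0.217 + 0.203 + 2.138) / 4 = 1.163.
- Var(log w) = 1.163 + 0.25² = 1.225.
- s = 0.6: 1.225 / (1.225 + 0.36) = 77%.
- s = 1.0: 1.225 / (1.225 + 1.00) = 55%.

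A second model takes weights log-uniform over 2.5–50 kg, a fixed time, and a rate varying 2-, 4- or 8-fold. It gives 95%, 82% and 67%. For example, (ln 20)²/12 = 0.748 and (ln 8)²/12 = 0.360, so 0.748 / 1.108 = 67%.

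**4. The same share within a cohort.**

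- With log-SD of weight 0.25: 0.0625 / 0.4225 = 15% at s = 0.6, and 0.0625 / 1.0625 = 6% at s = 1.0.
- For a wide cohort with assumed weights log-uniform over 10–40 kg, Var(log w) = (ln 4)²/12 = 0.160. The share is 0.160 / 0.520 = 31% at s = 0.6 and 0.160 / 1.160 = 14% at s = 1.0.
- If instead time is fixed and the rate varies 2-, 4- or 8-fold, the 10–40 kg cohort gives 80%, 50% and 31%. An assumed 30–50 kg cohort gives 35%, 12% and 6%.

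Weight therefore dominates the overall mg summary under both models. Within a cohort it may or may not.

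**The case against.** The best reply is that the plan already has what matters. Infusion rate in μg/kg/min is the first-named component of the primary dose endpoint, and number of titrations sits beside it. SAP 8 gives initial, maximum, median and average rates per kg. Every summary is also shown by cohort, the analysis is descriptive, and DSMB review and dose adjustment proceed cohort by cohort. Nothing makes the pooled mg figure the basis of a dosing conclusion. All of this stands. A reader might infer that the trial's dosing results as a whole mainly reflect body weight, or that mg does so even inside each age cohort. The documents do not support the first, because two of the three primary components do not scale with weight. The calculation does not support the second, because within-cohort shares run from 6% to 80% depending on assumptions.

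On the formula, the output unit is explicit, the definition names no unit for total dose at that point, and a programmer would probably notice values a thousandth of the neighbouring rates. That makes a wrong table unlikely; it does not make the definition correct.

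On the graphs, each shows one patient. SAP 8 scales by a single baseline weight, so mg/h is μg/kg/min times a constant and the pattern is unchanged. Protocol 1.2.2 also cites the labelled adult range in mg/h. Only comparison between patients is harder, which is a matter of presentation.

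**Conclusion.** Two limited points hold.

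- The average-rate definition in SAP 8 is wrong as written by a factor of 1,000 for its stated unit. This is certain on the text and needs no assumption. It affects an exposure variable and no efficacy endpoint.
- The overall summary of total dose in mg, one of three primary dose components, is driven largely by weight. The 20-fold ratio is exact for equal per-kg dosing over 2.5–50 kg, but that is the range simulated, not the range enrolled. The 55% to 77% share rests on the assumed weights and spreads, and on dose per kg being independent of weight. If dose per kg changes with age, the mg figure mixes that change with body size and cannot separate them.

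Neither point shows that weight-adjusted dosing results are missing from the plan, or that the by-cohort mg summaries are dominated by weight.

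**What to change.** - **SAP 8:** multiply by 1,000 in the average-rate definition, or state that total dose enters this formula in μg.
- **SAP 10.1 and SAP 8:** add total dose per kg of baseline weight beside total dose in mg, and use the per-kg figure for the overall summary.
- **SAP 10.2.5 (optional):** label the individual graphs in μg/kg/min, alone or beside mg/h, so that patients can be compared.

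The cost is a few words of SAP text and one derived variable. Weight is already collected at screening and SAP 8 already uses baseline weight. No dose, titration rule or data collection changes.
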